11.18 Discontinuation Criteria and Procedures

According to the Declaration of Helsinki, all subjects have the right to withdraw from a study at any time, regardless of their reasons. In addition, it is the right of the Investigator to remove subjects from the study as a result of AEs, protocol violation, or any other reason.

11.18.1 Premature Termination of Study/Closure of Study Sites

The study may be terminated prematurely if new toxicological findings or results affecting the safety of the subjects become available. A site may be closed prematurely if recruitment is too slow, poor quality data is produced, or there is evidence of attempted or proven fraud.

In the event the Sponsor prematurely terminates the study, the Investigator will promptly notify the Institutional Review Board (IRB).

12 EVALUATION AND REPORTING OF ADVERSE EVENTS

12.1 Adverse Event (AE) Definitions

An AE is defined as any untoward medical occurrence in a subject administered a medicinal product and which does not necessarily have to have a causal relationship with this treatment. AEs occurring after the initiation of the treatment are referred to as treatment emergent adverse events (TEAEs). An AE can therefore be any unfavorable and unintended sign (for example, an abnormal laboratory finding), symptom, or disease temporally associated with the use of a medicinal product, whether or not considered related to this medicinal product.

A suspected adverse reaction is any AE for which there is a reasonable possibility that the drug caused the AE. 'Reasonable possibility' means there is evidence to suggest a causal relationship between the drug and the AE. A suspected adverse reaction implies a lesser degree of certainty about causality than adverse reaction, which means any AE caused by a drug.

An AE may be:

- A new illness,
- Worsening of a concomitant illness,
- An effect of the study medication including comparator; it could be an abnormal laboratory value as well as a significant shift from baseline within normal range which the Principal Investigator or medical qualified designate considers to be clinically important.

Surgical procedures themselves are not AEs. They are therapeutic measures for conditions that required surgery. The condition for which the surgery is required is an AE, if it occurs or is detected during the study period. Planned surgical measures permitted by the clinical study protocol and the condition(s) leading to these measures are not AEs, if the condition(s) was (were) known before the start of study treatment. In the latter case, the condition should be reported as medical history.

A serious adverse event (SAE) or reaction is any untoward medical occurrence that at any dose:

- Results in death,
- Is life-threatening,
- Requires inpatient hospitalization or prolongation of existing hospitalization,
- Results in persistent or significant disability or incapacity (defined as a substantial disruption of a person's ability to conduct normal life functions),
- Is a congenital anomaly or birth defect,
- Is an important medical event (including development of drug dependence or drug abuse) that may jeopardize the subject or may require intervention to prevent one of the other outcomes listed above (according to medical judgment of the Principal Investigator).

12.1.1 Severity Assessment

All AEs will be graded as mild, moderate, or severe according to the following definitions:

- Mild: Causing no limitation of usual activities; the subject may experience slight discomfort.
- Moderate: Causing some limitation of usual activities; the subject may experience annoying discomfort.
- Severe: Causing inability to carry out usual activities; the subject may experience intolerable discomfort or pain.

Every effort will be made to obtain an adequate evaluation of the severity.

12.1.2 Causality Assessment

Investigators are required to assess the causal relationship (i.e., whether there is reasonable possibility that the study drug caused the event) using the following definitions:

- **Unrelated**: another cause of the adverse event is more plausible; a temporal sequence cannot be established with the onset of the adverse event and administration of the study agent; or a causal relationship is considered biologically implausible.
- **Possibly Related**: There is a clinically plausible time sequence between onset of the adverse event and administration of the study agent, but the adverse event could also be attributed to concurrent or underlying disease, or the use of other drugs or procedures. Possible related should be used when the study agent is one or several biologically plausible adverse event causes.
- **Definitely Related**: The adverse event is clearly related to use of the study agent.

12.2 Routine Reporting

For the purposes of this study, the period of observation of AEs extends from the signing of the consent at the screening visit until the follow-up call. During this period, all AEs spontaneously reported by the subject, observed by the clinical staff, or elicited by general questioning will be recorded and reported in the CRF.

Any AE which remains unresolved as of the last visit will require an evaluation and follow-up until the AE has been resolved or a reasonable explanation for its persistence found, or is deemed mild and safely resolving.

In the case of AEs deemed related to the Investigational Product, every effort will be made to determine the final outcome.

It is the Investigator's responsibility to ensure subjects experiencing AEs receive appropriate follow-up, treatment where required, and that every action is well documented.

Subjects will be questioned on their health status at the beginning of the study period and before the departure from the clinical site. Open-ended questions will be asked.

Classification will be performed by System Organ Class (SOC) and Preferred Term (PT) using the Medical Dictionary for Regulatory Activities (MedDRA), version 19.0 or higher.

In general, AEs occurring secondary to other events (e.g., clinical sequelae or a cascade of events) should be identified by their primary cause. For example, if severe vomiting is known to result in dehydration, it is sufficient to record only vomiting as SAE or AE in the CRF. However, medically significant AEs occurring secondary to an initiating event that are separated in time should be recorded as independent events on the CRF.

Pregnancy in a female subject on the study shall be reported to the sponsor within 24 hours of the knowledge of its occurrence by the Principal Investigator or designee (for pregnancies occurring during the course of the study or immediately following the end of the study). Because of the possibility that the fetus/embryo could have been exposed to the study drug through the parent and for the subject's safety, the pregnancy will be followed up to determine its outcome, including spontaneous or voluntary termination, details of birth, presence or absence of any birth defects, congenital anomalies, or maternal and/or newborn complications.

The pregnancy will be recorded and reported by the Principal Investigator or designee to the sponsor. Pregnancy follow-up will also be properly recorded to ensure quality and completeness of the data belonging to the study drug and will include an assessment of the possible causal relation between the study drug and any pregnancy outcome. Any SAE experienced during pregnancy will be reported on a SAE Report Form.

12.3 Serious Adverse Event Reporting

The sites will notify the sponsor of any SAE, without regard to causality, within 24 hours after becoming aware of its occurrence.

If, during follow-up, any non-serious AE worsens and eventually meets the criteria for an SAE, that AE should be recorded as a new SAE.

The initial SAE report must be as complete as possible, including details of the current illness and SAE, and an assessment of the causal relationship between the event and the investigational product(s). Information not available at the time of the initial report (e.g., an end date for the AE, laboratory values received after the report, or hospital discharge summary) must be documented. All follow-up information must be reported as soon as the relevant info is available.

The notification should be directed to the following sponsor representatives:

[name].
Medical Director, Mary Rutan Hospital Department of Pathology
[name]
[name]
[contact]
Office: [contact]
[contact]

An SAE will be considered "unexpected" if the AE is not listed in the investigator brochure or is not listed at the specificity or severity that has been observed; or, if an investigator brochure is not required or available, is not consistent with the risk information described in the general investigational plan or elsewhere in the current application. "Unexpected," as used in this definition, also refers to AEs that are mentioned in the Investigator's Brochure as occurring with a class of drugs or as anticipated from the pharmacological properties of the drug, but are not specifically mentioned as occurring with the particular drug under investigation.

The sites will determine whether any serious unexpected related AE must be reported to the IRB. If so, the event will be reported via fax or email within 15 calendar days of the investigator or staff becoming aware of the event.

The sponsor will determine whether the SAE must be reported in an expedited manner to the appropriate regulatory agencies. If so, the sponsor will report the event to the appropriate regulatory agencies, and all participating investigators.

If reports of any new and unexpected AEs become available to the sponsor during the clinical portion of this study (related or not to the present study), the sponsor must advise the sites of those events.

13 STATISTICAL METHODS

13.1 Determination of Sample Size

This study is designed to test non-inferiority of tolperisone doses relative to placebo, with a cyclobenzaprine test versus placebo to confirm the sensitivity of the simulator to detect treatment effects. The following assumptions were made in the sample size computation: (a) within-subject standard deviation for SDLP is approximately 6 cm; (b) the true difference between tolperisone doses and placebo is 0; and, (c) the non-inferiority (NI) margin is proposed to be 4.4 cm, which is the effect seen with 0.05% of BAC with this driving simulator scenario. Under these assumptions, a sample of 30 subjects would provide in excess of 90% power to establish non-inferiority of tolperisone compared to placebo on any given dosing day in terms of the primary end point, SDLP. This sample size is considered more than adequate to detect cyclobenzaprine differences from placebo, which are anticipated to exceed the NI margin.

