8 SUBJECT DEFINITION

A sufficient number of subjects will be enrolled to ensure a total of 30 subjects will complete all dosing periods, including the driving assessment. Individuals are eligible for this study if they meet all inclusion and no exclusion criteria. The criteria below will be assessed at the Screening visit.

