9 STUDY DESIGN

9.1 Summary of Study Design

This will be a randomized, placebo-controlled, multiple-dose 3-way cross-over study of the safety and cognitive effects of multiple doses of tolperisone administered TID in 30 male and female healthy volunteers. Treatment groups include 450 mg tolperisone (i.e., 150 mg administered three times daily), 30 mg cyclobenzaprine (i.e., 10 mg administered three times daily), and placebo.

Subject participation will be approximately 3 weeks as outpatients with 3 days each week as overnight clinic participants.

Subjects will be screened within 28 days prior to Treatment Period 1 (Visit 2) for eligibility for participation in the study. The Familiarization and Practice drives on the driving simulator must be completed no more than 21 days prior to Treatment Period 1.

Subjects meeting all inclusion/exclusion criteria will then be admitted to the clinic on Day -1 to be evaluated for continued eligibility. Subjects will perform a practice trial with the driving simulator and the cognitive function test.

Subjects will be dosed on the morning of Day 1. Approximately one hour after the second dose on Day 1, subjects will be administered the cognitive test, followed by the driving simulator examination.

[figure not shown]
On the morning of Day 2, prior to dosing, subjects will be readministered the cognitive test and driving examination to assess residual next day effects.

Subjects will repeat cognitive testing and the driving examination on the morning of Day 3, after administration of the AM study medication, to evaluate the cumulative effects of 3 days of dosing.

Subjects will be discharged on Day 3 with instructions to return to the clinic on Day 7 and Day 14 to repeat the above procedures with the second and third treatments.

A follow-up phone call will be conducted 1 week (± 3 days) following discharge from the clinic on Day 17 to assess for continued safety.

Schematic of Design:

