9.3 Subject Assignment

Prior to dosing, subjects will be randomly assigned to one of 6 treatment sequences (one for each permutation of treatment groups) and dosed with study medication (tolperisone, cyclobenzaprine or placebo) based upon a randomization scheme provided by Cognitive Research Corporation. Only the qualified person(nel) assigned to prepare and administer the study treatment will have access to the randomization schedule and dispensing records during the study period.

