13.3 Statistical Analysis – General Considerations

This section describes the general approaches planned to analyze the data from this study. Additional details of the planned analyses outlined here, will be further described in the SAP.

Doses of tolperisone will be considered non-inferior to placebo if the upper 95% confidence limit on the difference in SDLP between that dose and placebo is less than 4.4 cm (the NI margin). Cyclobenzaprine comparisons to placebo are to assess assay sensitivity and no adjustment to

alpha levels will be made for either the comparison of cyclobenzaprine to placebo or tolperisone, or for secondary endpoints or analyses. Formal statistical tests (where performed) will be two-sided and testing at the $\alpha=0.05$ level of significance.

The sequence of testing to control for multiplicity associated with comparisons of tolperisone to placebo (to assess NI) on multiple days is Day 1 (single-dose) , followed by Day 3 (steady-state), followed by Day 2 (residual effect). Tolperisone will be considered NI to placebo if prior comparisons (at time points in the sequence provided, above) also indicate non-inferiorty.

In general, categorical variables will be summarized by the count (N) and percentage of subjects (%). Continuous variables will be summarized by the number of non-missing observations (N), mean, standard deviation (SD), median, minimum, and maximum values.

All study data are to be displayed in the data listings.

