6.1 STATISTICAL METHODOLOGY

6.1.1 DETERMINATION OF SAMPLE SIZE

This study is designed to test non-inferiority (NI) of tolperisone doses relative to placebo, with a cyclobenzaprine test versus placebo to confirm the sensitivity of the simulator to detect treatment effects. The following assumptions were made in the sample size computation: (a) within-subject standard deviation for SDLP is approximately 6 cm; (b) the true difference between tolperisone doses and placebo is 0; and, (c) the NI margin is proposed to be 4.4 cm, which is the effect seen with 0.05% of blood alcohol content (BAC) with this driving simulator scenario. Under these assumptions, a sample of 30 subjects would provide in excess of 90% power to establish NI of tolperisone compared to placebo on any given dosing day in terms of the primary end point, SDLP. This sample size is considered more than adequate to detect cyclobenzaprine differences from placebo, which are anticipated to exceed the NI margin.

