6.1.4 MULTIPLE COMPARISONS

There are a number of comparisons of interest from which conclusions with respect to the NI of tolperisone vs. placebo will result. Initially, the statistical significance of the cyclobenzaprine vs. placebo ($p<0.05$) comparison is necessary to validate the experiment as having the ability to detect effects (i.e., assay sensitivity).

Subsequently, the NI of tolperisone to placebo (for initial dose, next day residual, and steady-state dose comparisons) will result in a conclusion of NI of tolperisone relative to placebo. For NI conclusions, the alternative hypothesis (of NI) will be considered established if the upper 95% confidence limit for tolperisone vs placebo difference is less than the pre-specified NI margin of 4.4 cm.

Cyclobenzaprine comparisons to placebo are to assess assay sensitivity and no adjustment to alpha levels will be made for either the comparison of

cyclobenzaprine to placebo or tolperisone, or for secondary endpoints or analyses.

The sequence of testing to control for multiplicity associated with comparisons of tolperisone to placebo (to assess NI) on multiple days is Day 1 (single-dose), followed by Day 3 (steady-state), followed by Day 2 (residual effect). Tolperisone will be considered NI to placebo if prior comparisons (at time points in the sequence provided, above) also indicate NI.

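### The stated power above 90% does not follow from the stated inputs: a within-subject SD of 6 cm, a 4.4 cm margin and 30 subjects give about 80% per day

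*Protocol*

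**What the plan says.** Protocol 13.1 and SAP 6.1.1 list the same assumptions: "within-subject standard deviation for SDLP is approximately 6 cm", a true tolperisone–placebo difference of 0, and a non-inferiority margin of 4.4 cm. From these the protocol concludes that "a sample of 30 subjects would provide in excess of 90% power to establish non-inferiority of tolperisone compared to placebo" on any given dosing day, and the SAP says the same. Neither gives a formula, a correlation between periods, degrees of freedom or the SD of a paired difference.

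The trial is a "randomized, placebo-controlled, multiple-dose 3-way cross-over study" (Protocol 9.1), so tolperisone is compared with placebo within subjects. Thirty is a count of completers, because Protocol 8 enrols enough "to ensure a total of 30 subjects will complete all dosing periods, including the driving assessment".

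The decision rule is in Protocol 13.3: "Doses of tolperisone will be considered non-inferior to placebo if the upper 95% confidence limit on the difference in SDLP" is below 4.4 cm. The same section makes formal tests two-sided at 0.05. Protocol 13.6 and SAP 6.5.1 specify 95% confidence intervals for the differences in least squares means.

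**The concern.** In crossover usage, a within-subject SD describes the residual variation of one measurement around the subject's own level. A difference between two periods carries that variation twice, so its SD is √2 times larger. With 6 cm as the within-subject SD, the difference has an SD of about 8.5 cm, and 30 subjects do not appear to give 90% power against a 4.4 cm margin.

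This paragraph is the only justification of the sample size. If the figure is wrong, the sponsor is accepting about twice the implied risk of failing to show non-inferiority for a drug with no effect on driving. The remark that the sample is more than adequate for cyclobenzaprine uses the same SD, and SAP 6.1.4 makes a significant cyclobenzaprine–placebo difference a precondition for interpreting the experiment.

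**Working it through.** **Inputs**

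- Within-subject SD, σ_w = 6 cm; true difference 0; margin 4.4 cm; n = 30 completers (Protocol 13.1 and 8; SAP 6.1.1).
- Limit: upper bound of the two-sided 95% interval, i.e. one-sided 0.025 (Protocol 13.3 and 13.6; SAP 6.1.3 and 6.5.1). A one-sided 95% bound is tried as the lenient alternative.

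**Standard error**

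- SD of the paired difference = 6 × √2 = 8.49 cm.
- SE = 6 × √(2/30) = 1.549 cm.
- Margin / SE = 4.4 / 1.549 = 2.840.

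**Attempt to reproduce the stated figure**

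The normal approximation is Φ(2.840 − 1.960) = 81.1%. The t versions use the noncentral t distribution with noncentrality 2.840. The degrees of freedom are 56 for the residual of a three-period crossover (90 observations − 1 − 29 for subjects − 2 for periods − 2 for treatments) or 29 for a paired comparison.

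| Reading of the inputs | Normal | t, 56 df | t, 29 df |
|---|---|---|---|
| σ_w = 6, two-sided 95% interval | 81.1% | 79.7% | 78.4% |
| σ_w = 6, one-sided 95% bound | 88.4% | 87.7% | 87.0% |
| 6 cm is the SD of the paired difference, two-sided 95% interval | 98.0% | 97.7% | 97.3% |

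In the last row, SE = 6/√30 = 1.095 cm and margin / SE = 4.017. The first two rows keep the SD as labelled, and neither exceeds 90%.

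**What 90% would need (two-sided 95% interval)**

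- At σ_w = 6 cm: 40 completers by the normal approximation, 41–42 by t.
- At 30 completers: σ_w of about 5.2 cm with 56 df.

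**All three days**

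SAP 6.1.4 says that non-inferiority "for initial dose, next day residual, and steady-state dose comparisons) will result in a conclusion of NI of tolperisone relative to placebo", and tests the days in the order 1, 3, 2. The documents give no between-day correlation of the differences, so it is assumed here. Simulating paired t intervals (29 df) gives a chance of success on all three days of about 48% at correlation 0, 58% at 0.5 and 70% at 0.9. With 56 df, independent days give 0.797³ = 51%, and perfectly correlated days give the single-day 80%.

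**Cyclobenzaprine versus placebo**

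With the same SE and 56 df, power is about 80% if the true effect is 4.4 cm. For illustration, it is about 89% at 5 cm, 94% at 5.5 cm and 97% at 6 cm.

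**The case against.** The strongest reply is that the label is wrong and the power is right. If 6 cm is the SD of the paired difference, power is 97–98%. If it is a total SD with a within-subject correlation of 0.3, power is about 91–92%. No formula is given, so the documents do not exclude a mislabelled input. This stands as a caveat on where the error lies, but it does not rescue the text. Both documents attach the SD to SDLP itself, and both speak expressly of differences elsewhere when they mean them (Protocol 13.6, SAP 6.5.1). Under either alternative the label still has to be corrected in two places.

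A second reply is that the plan never says whether the upper 95% limit is one- or two-sided. That is true, and the one-sided reading narrows the shortfall to about 2–3 points. It does not remove it, and the two-sided tests and 95% intervals point the other way. Nor does the word approximately help much: the SD would have to fall to about 5.2 cm.

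The replies on the side points have more force. The power claim is expressly per day, and under the fixed sequence a Day 1 conclusion does not depend on the later days. The joint figures rest on assumed correlations, so the absence of a three-day figure is not an arithmetic error. The sponsor also expects the cyclobenzaprine effect to exceed the margin, so 80% is the floor of that assumption; the adequacy remark is not shown to be wrong.

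Finally, the power statement does not enter the estimate, the interval, the margin or the decision rule. A wrong figure causes no bias and no inflation of type I error. The harm is to the justification of the sample size and to the sponsor's view of its own risk.

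**Conclusion.** The concern holds. On the inputs as written, power per dosing day is about 80% (78.4–81.1% across the methods tried), against a stated figure above 90%. The chance of missing non-inferiority on a given day with a truly inert drug is therefore about 20%, at least double what the plan implies. The conclusion assumes that 6 cm is the within-subject SD of SDLP, as both documents say, that 30 subjects complete, and that the true difference is 0. It does not depend on the sidedness of the limit, since the lenient reading also falls short. Either the SD label or the power figure is wrong, and only the sponsor can say which. The three-day and cyclobenzaprine figures are conditional and are not needed for this conclusion.

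**What to change.** Correct Protocol 13.1 and SAP 6.1.1 in the same way, leaving the sample size, margin and decision rule as they are:

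1. State which SD the 6 cm is.
   - If it is the within-subject SD of SDLP, restate power as about 80% on any given dosing day.
   - If it is the SD of the within-subject tolperisone–placebo difference, relabel it and restate power as about 97%.
2. State, there and in Protocol 13.3 and SAP 6.1.4, that the limit is the upper bound of the two-sided 95% confidence interval.
3. Give the method and degrees of freedom so that the figure can be reproduced.
4. Add the power for all three days in sequence, with the assumed between-day correlation. This supplements the per-day figure, which is the one in error.

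The cost is wording only, with no extra subjects and no change in conduct. If 6 cm is the within-subject SD, the price is a less favourable figure on record.

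### The stated power of over 90% on any dosing day is at best that of one stand-alone comparison; under the written testing order and the printed inputs, power is about 61–75% for Day 3 and 48–72% for Day 2

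*Protocol*

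**What the plan says.** **Sizing.** Protocol 13.1 assumes that "within-subject standard deviation for SDLP is approximately 6 cm", that "the true difference between tolperisone doses and placebo is 0" and that "the non-inferiority (NI) margin is proposed to be 4.4 cm". From these it claims that 30 subjects give "in excess of 90% power to establish non-inferiority of tolperisone compared to placebo on any given dosing day". SAP 6.1.1 uses the same inputs and claims "in excess of 90% power to establish NI of tolperisone compared to placebo on any given dosing day". Protocol section 8 plans for 30 completers, so no allowance for dropout is needed. Neither sizing section mentions the testing order, and no between-day correlation appears in either document.

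**Decision rule.** Under Protocol 13.3 a day passes if the upper 95% confidence limit for tolperisone minus placebo is below 4.4 cm. Formal tests are two-sided at 0.05.

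**Testing order.** Protocol 13.3 puts Day 1 first, "followed by Day 3 (steady-state), followed by Day 2 (residual effect". SAP 6.1.4 repeats the order and adds: "Tolperisone will be considered NI to placebo if prior comparisons (at time points in the sequence provided, above) also indicate NI".

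**Assay sensitivity.** SAP 6.1.4 places cyclobenzaprine versus placebo (p<0.05) ahead of the NI conclusions and says that this "comparison is necessary to validate the experiment as having the ability to detect effects". It does not say on which day or days the comparison must succeed.

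**The concern.** The sizing sentence speaks of power to establish NI. Under the written rule, a Day 2 interval lying wholly below 4.4 cm establishes nothing if Day 1 or Day 3 failed. Only Day 1 can carry a single-test power, and even that is subject to the SAP's cyclobenzaprine condition. For Day 3 the relevant quantity is the probability that two comparisons pass, and for Day 2 that all three pass. Neither probability is reported.

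The primary objective (Protocol 7.1, SAP 3.1) names all three assessments. The next-day residual effect comes last in the order, so when the single-day powers are equal it has the lowest power of the three. If a Day 3 or Day 2 conclusion is missed, a reader who has only the printed figure would judge that miss against a power that the design may not have.

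**Working it through.** **1. Inputs.** From Protocol 13.1 and 13.3: SD 6 cm, true difference 0, margin 4.4 cm, n = 30, two-sided 95% interval (one-sided 0.025 for NI). The between-day correlation ρ of the estimated tolperisone–placebo difference is an assumption, ranged from 0 to 0.9 and taken as equal for all pairs of days.

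**2. The plan's own figure, one day alone.** Power = Φ(margin/SE − 1.960).

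- *6 cm as labelled, a within-subject SD.* SE = 6 × √(2/30) = 1.549. Then 4.4/1.549 = 2.840, and 2.840 − 1.960 = 0.880, so Φ = 81.1%. The noncentral t gives 78.4% with 29 df (paired test) and 79.7% with 56 df (crossover residual: 90 − 30 − 2 − 2). A one-sided 95% limit would give 88.4% (normal) or 87.0% (t, 29 df). None of these exceeds 90%.
- *6 cm as the SD of the paired difference.* SE = 6/√30 = 1.095. Then 4.4/1.095 = 4.017, and 4.017 − 1.960 = 2.057, so Φ = 98.0% (t, 29 df: 97.3%). Of the readings tried, only this one reproduces the printed claim.

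**3. Adding the testing order.** Power for Day 3 = P(Days 1 and 3 pass). Power for Day 2 = P(all three days pass). Under independence these are p² and p³; for example 0.90² = 0.81 and 0.90³ = 0.729. For ρ > 0 they come from an equicorrelated multivariate normal.

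| Single-test basis | One day | Day 3 at ρ = 0 / 0.5 / 0.9 | Day 2 at ρ = 0 / 0.5 / 0.9 |
|---|---|---|---|
| Within-subject SD 6, t with 29 df | 78.4% | 61.4 / 66.5 / 73.1% | 48.2 / 58.7 / 70.2% |
| Within-subject SD 6, t with 56 df | 79.7% | 63.5 / 68.3 / 74.7% | 50.6 / 60.7 / 71.8% |
| Each test exactly 90% (hypothetical) | 90.0% | 81.0 / 83.2 / 86.9% | 72.9 / 78.2 / 85.0% |
| Paired-difference SD 6, t with 29 df | 97.3% | 94.6 / 95.0 / 96.2% | 92.0 / 93.2 / 95.4% |

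Paired-t simulation of both SD readings at ρ = 0, 0.5 and 0.8 (60,000 trials per setting) agreed with this method to within about 1 point.

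**4. Separating the two causes.** Take the printed inputs with 56 df and ρ = 0.5. The single-day calculation accounts for 90 − 79.7 = 10.3 points of the shortfall. The testing order takes a further 79.7 − 68.3 = 11.4 points for Day 3 and 79.7 − 60.7 = 19.0 points for Day 2.

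**5. The cyclobenzaprine condition, as illustration only.** The documents give no effect size beyond expecting it to exceed the margin.

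- At within-subject SD 6, with the condition applied on Day 1 only, the probability of meeting it and passing Day 1 NI is about 60%, 69%, 77% and 80% for cyclobenzaprine effects of 4.4, 5, 6 and 8 cm.
- If 6 cm is the paired-difference SD, the condition must hold on all three days and ρ = 0.5, power for all three NI conclusions is about 88% at 4.4 cm, 92–93% at 5 cm and 94% at 6 cm. Without the condition it is about 94%.

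**The case against.** **The wording is per-day, and per-day power is an ordinary thing to report.** This stands in part. Neither sizing section claims a power for the ordered sequence, so the sequence itself is an unreported quantity rather than a wrong sum. But the sentence is about establishing NI, and under the written rule a stand-alone pass on Day 3 or Day 2 does not do that.

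**The documents say more than 90%, not 90%.** This stands, and it limits the point. A reader might infer that power for Day 3 and Day 2 must fall well below the printed figure whatever the inputs. The documents do not support that. If 6 cm is the SD of the paired difference, every step of the tolperisone sequence stays at 92% or more before the cyclobenzaprine condition, and the printed sentence is true for all three days. Against this, both documents label the 6 cm as a within-subject SD for SDLP, so that reading replaces the printed label.

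**The same subjects drive on all three days, so positive correlation is plausible.** This stands. Independence is the worst case among non-negative correlations. With each test at exactly 90% and ρ = 0.9, the loss is about 3 points for Day 3 and 5 for Day 2. A reader might also infer that a non-sedating drug would miss the Day 2 conclusion one time in four or five. That holds only at exactly 90% per test and ρ of about 0 to 0.5 (27% to 22%). At ρ = 0.9 it is 15%, about one in seven.

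**Part of the shortfall belongs to the SD, not to the testing order.** This stands, as step 4 of the working shows. Resolving the SD would still not supply the missing power for Day 3 and Day 2.

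**The cyclobenzaprine figures are speculative.** This stands. They rest on an effect size and a choice of day that the documents do not give, and they are not part of the headline numbers.

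**Conclusion.** The point holds conditionally. The printed figure is at best the power of one stand-alone comparison, and the power to conclude NI on Day 3 or Day 2 under the written order is not reported.

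- **On the inputs as printed:** about 78–80% for a single day, 61–75% for Day 3 and 48–72% for Day 2. The claim of more than 90% is then not met on any day.
- **With each test at exactly 90%:** about 81–87% for Day 3 and 73–85% for Day 2.
- **With 6 cm as the paired-difference SD:** about 95–96% for Day 3 and 92–95% for Day 2, before the cyclobenzaprine condition. The claim is then met.

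These results assume 30 completers, a true difference of 0, a two-sided 95% interval and an equal between-day correlation of 0 to 0.9. The SAP's cyclobenzaprine condition can only lower them. By how much depends on an effect size that is not stated.

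**What to change.** In Protocol 13.1 and SAP 6.1.1:

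1. State whether the 6 cm is the within-subject SD of SDLP or the SD of the tolperisone–placebo paired difference, and recompute the single-test power on that basis.
2. Give the single-test power for Day 1 only.
3. Give the power to conclude NI on Day 3 (Days 1 and 3 both pass) and on Day 2 (all three pass) under the written testing order, over a stated range of between-day correlations.
4. Note that the SAP 6.1.4 cyclobenzaprine condition can lower these figures further, by an amount that depends on the cyclobenzaprine effect.

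Leave the sample size, testing order and analysis as they are. The cost is a few sentences and one short calculation. The only downside is that the stated power may be less favourable.
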